This study is a randomized, placebo-controlled, single blind clinical trial. Seventy patients with ESRD on chronic HD and a functioning AVF will be recruited. Consent form will be obtained. History and physical, dialysis parameters and laboratory data (CBC, CMP, PTT & INR) will be obtained throughout the study. The following data will be documented on each patient: 1-Age/gender/race/body weight/cause of ESRD 2-Vintage of HD 3-Time since access was placed 4-Type and place of access and blood flow rate of access 5-History of prior access problems 6-Comorbid conditions (Hypertension, coronary artery disease, Diabetes Mellitus, Bleeding problems, peripheral vascular disease). 7-Current medications (Coumadin, Erythropoiesis stimulating agents, heparin, other antiplatelets, digoxin, statins). Patients will be randomized into two groups to receive: Group 1: Ticagrelor 90 mg PO BID Group 2: Placebo drug PO BID.

Subjects will have a screening visit and if they qualify for the study they will have 18 additional visits. All of these visits will occur while the subjects are at their normal dialysis treatment. Subjects will be randomized to either the Ticagrelor group or the placebo group. Subjects will be on study medication for 6 months then they will have a follow up period off drug for 6 months. Subjects will be seen twice a month while on study medication and once a month in the follow up period. While the subjects are on study medication we will assess any side effects of the study medication and put their relation to the study drug at each study visit. We will use clinical monitoring as suggested by Beathard (21). We will document the subject's adherence to the study, if they are hospitalized and what caused their hospitalization. A monthly intra-access flow will be obtained using ultrasound dilution by transonics as part of standard of care. Any change in the clinical assessment of the access, prolonged bleeding (>20 minutes) after removal of needles, trend of decreasing intra-access blood flow as determined by transonic (> 25% or original flow), or an access flow rate < 400 ml/min, will prompt a referral for a fistulogram. If confirmed stenosis (>50% stenosis of the access diameter) an intervention (angioplasty) will be performed. This intervention is part of the subject's standard of care.

Background

1. Provide the scientific background, rationale and relevance of this project.

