Due to the pilot nature of this study, formal power analysis and sample size estimation is not essential. Nevertheless, we attempted to estimate the potential treatment efficacy in this study. We considered the outcome measure for efficacy evaluation is the time to first stenosis event during the study period. From our recent clinical data, it was estimated that approximately 36% of dialysis patients experienced stenosis event at one-year follow-up. We would expect that patients in the new drug arm would have 10% stenosis event rate at one-year follow-up, compared to the 36% stenosis event rate in the placebo group. With these considerations, the analysis of stenosis-free survival will require at least 21 events, which is the number of events needed for one-sided log-rank test at 5% significance level to have 80% power to show statistically significant difference when the true hazard ratio is 0.236. This estimation will result in that approximately seventy patients will be needed and evenly randomized into each study arm (35 patients in Ticagrelor and 35 in placebo). This is an open-label study. Upon completion of all the required screening assessments, eligible patients will be randomly assigned to the study drug or placebo at 1:1 ratio with a block size of 20 in accordance with the randomization schedule. The randomization schedule will be provided by the Department of Public Health, School of Medicine. Patients will be identified by unique subject identifier that will remain consistent for the duration of the study. The active study period is 6 months followed by 6 months of monitoring, and accrual rate is approximately 12 patients per month. To compensate for an estimated drop-out rate of 25%, we will recruit 88 patients to the study.

4. What is your plan for primary variable analysis?

We have recruited/consented a total of 54 subjects into this study. We have enrolled a total of 43 patients into the study, 23 in the Ticagrelor treatment arm and 20 in the placebo arm. We will evaluate the safety of Ticagrelor in hemodialysis patients with AVF vascular access by tabulating adverse events and severe adverse events for the two study arms, and the difference between the two arms will be tested by chi-square test.

5. What is your plan for secondary variable analysis?

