For the secondary outcome, i.e., time to the first stenosis event, we will compare stenosis-free survival of Ticagrelor versus placebo using the Kaplan-Meier method. Survival probabilities and corresponding 95% confidence interval (CI) will be calculated at landmark time points for each arm, and survival difference between the two arms will be evaluated using a one-sided log-rank test stratified by the history of stenosis. Further, a stratified Cox proportional-hazards model will be used to derive the hazard ratio and 95% CI between the two regimens.

6. Have you been working with a statistician in designing this protocol?

Yes

IRB-HSR# 17224: Randomized, Placebo-controlled, Single Blind, Trial to Determine the Safety and Efficacy of Ticagrelor for Maintaining Patency of Arterio-Venous Fistulae Created for Hemodialysis

IF YES, what is their name?

[name]

Biomedical Research

1. What will be done in this protocol?

Subjects will be in this study for 1 year. Up to eighty eight patients with ESRD on chronic HD and a functioning AVF will be enrolled. For statistical purposes we will need to have seventy people complete the study. Consent form will be obtained. History and dialysis parameters will be taken at the screening visit. At the screening visit we will also be collecting a serum sample to perform a pregnancy test on female subjects of child bearing potential. This will be collected in a 3.5ml gold top serum separating tube. Study participants will be on the study medication (Ticagrelor) or placebo for six months (Visit 1 to Visit 12). Subjects will take the study medication twice a day. They will take it once in the morning and once in the evening. We will also instruct them to try and take it around the same times each day if possible. We will be collecting study medication to check for compliance at Visits 3, 6, 9, and 12. There will be a follow up for these subjects for six months (Visit 13 to Visit 18). Subjects will have a physical performed at screening, visit 12 (this is the last visit when subjects are on medicine), and at visit 18 which is the end of the study. We will be looking at hemoglobin levels that are collected as standard of care two times a month. We will be collecting the bleeding time weekly as well. This will be done at all visits (screening to Visit 18) which we define as the time it takes for a subjects' access to stop bleeding.

The following data will be documented on each subject at screening:

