1-Age/gender/race/body weight/cause of ESRD

2-Vintage of HD

3-Time since access was placed

4-Type and place of access and blood flow rate of access

5-History of prior access problems

6-Comorbid conditions (Example: Hypertension, coronary artery disease, Diabetes Mellitus, Bleeding problems, peripheral vascular disease).

7-Current medications (Example: Coumadin, Erythropoiesis stimulating agents, heparin, other antiplatelets, digoxin, statins)

This data will be obtained from the dialysis computer system and will be verified with the subject.

8-Physical Exam

9-Vital signs (blood pressure, heart rate, and weight) will be obtained from the subject's dialysis record.

Adverse events and concomitant medications will be reviewed at each study visit. We will also note any access issues at each study visit.

Study Medication Stopping Rules for Prolonged Bleeding:

If post treatment bleeding time is prolonged more than 30 minutes we will stop the study drug and refer for fistulogram,

If bleeding still persists after fistulogram and intervention we will continue to hold the study drug and do work up for bleeding. We will continue to hold study drug for 5 days if signs of increased tendency for bleeding as recurrent Epistaxis > twice in one week, if any evidence of GI bleed, or if Hgb should drop > 1gm in one week. If the bleeding is believed to be drug related or it no resolution occurs the subject will be withdrawn from the study.

We will also hold study drug for 5 days if hemoglobin is consistently less than 8g/dL for 2 consecutive weeks, or hemoglobin dropping 1g/dL in one week.

IRB-HSR# 17224: Randomized, Placebo-controlled, Single Blind, Trial to Determine the Safety and Efficacy of Ticagrelor for Maintaining Patency of Arterio-Venous Fistulae Created for Hemodialysis

For a prolonged bleeding event standard practice will be applied, including: (prolonged bleeding is defined as bleeding more than 30 minutes)

- **Direct pressure.** Any bleeding that warrants an emergency department visit should be immediately controlled with the application of direct digital pressure to the puncture site for 5-10 minutes. Once the bleeding abates, the patient should be observed for rebleeding or early thrombosis for 1-2 hours.

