2.1 What are identified risks and plans to minimize risk

****Please Also Refer to the Investigator Brochure and the Package Insert for Brilinta/ Ticagrelor**

Adverse Events with Brilinta/Ticagrelor

Frequent complaints (seen in at least 3% of study participants) that have been reported during studies:

- Bleeding
- Dyspnea (Shortness of Breath)
- Cough
- Dizziness
- Nausea
- Atrial Fibrillation (Heart Rhythm Disorder)
- Hypertension (High Blood Pressure)
- Non-Cardiac Chest Pain

IRB-HSR# 17224: Randomized, Placebo-controlled, Single Blind, Trial to Determine the Safety and Efficacy of Ticagrelor for Maintaining Patency of Arterio-Venous Fistulae Created for Hemodialysis

- Diarrhea
- Back Pain
- Hypotension (Low Blood Pressure)
- Fatigue
- Chest Pain
- Headache

More Frequent complaints (seen in at least 6 to 7% of study participants) that have been reported during studies:

- Bradycardia (Slow Heart Rate)
- Elevated Serum Creatinine

There have also been cases of increased uric acid levels for subjects taking ticagrelor. A high uric acid level, or hyperuricemia, is an excess of uric acid in your blood. Uric acid is produced during the breakdown of purine, a substance found in many foods. Once produced, uric acid is carried in your blood and passes through your kidneys, where most of it leaves your body when you urinate. A high uric acid level may result in attacks of gout, but not everyone who has high uric acid gets gout, and not everyone with gout has high uric acid. Increased uric acid may also increase the chances of kidney stones. There is also an increased risk of severe bleeding for subjects taking ticagrelor. Due to the increase risk of severe bleeding there may be a risk of delay in any surgery that you may need while taking this study medication.

Expected Risks related to study participation.	Frequency
Reproductive Risks These are unknown at this time.	Minimized due to the requirements of this protocol.
Violation of subject’s privacy and confidentiality	Minimized due to the requirements of the privacy plan in this protocol

2.2 List by bullet format a summary of safety tests/procedures/observations to be performed that will minimize risks to participants:

- Study personnel will be checking on patients twice a month for six months while subjects are on study treatment and once a month while subjects are in the follow up visits.
- We will be monitoring the time it takes for the subject’s access to clot.
- AE monitoring at each visit

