3.1 Will all adverse events, as defined in section 1.1, be collected/recorded?

No

► IF NO, what criteria will be used?

Only adverse events that are deemed related AND serious

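### Heart rate and blood pressure, tied to harms the protocol lists, are named as data only at screening and enter no analysis, so a non-serious on-drug effect can be missed

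*Combined protocol and SAP*

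**What the plan says.** **Harms.** Data and Safety Monitoring Plan 2.1 has two frequency tiers. The higher, at least 6 to 7%, holds bradycardia and elevated serum creatinine. The lower, at least 3%, includes hypotension, hypertension and bleeding.

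**Collection.** In Biomedical Research item 1, under the lead-in "The following data will be documented on each subject at screening", item 9 reads "Vital signs (blood pressure, heart rate, and weight) will be obtained from the subject's dialysis record". Other text bears on later collection without naming vital signs:
- The opening summary says "History and physical, dialysis parameters and laboratory data (CBC, CMP, PTT & INR) will be obtained throughout the study".
- Biomedical Research item 1 says "Subjects will have a physical performed at screening, visit 12 (this is the last visit when subjects are on medicine), and at visit 18". It does not say what the physical contains.
- The timeline under Hypothesis to be Tested gives physical examination, laboratory and dialysis data in the 6-month follow-up.

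Vital signs are absent from the research procedures (Biomedical Research item 3) and from the safety observations in section 2.2.

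**Analysis.** Statistical Considerations item 4 evaluates safety by "tabulating adverse events and severe adverse events for the two study arms", with a chi-square test between arms. Item 5 covers time to stenosis only.

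**Recording.** Section 3.1 answers that not all adverse events are recorded: "Only adverse events that are deemed related AND serious". Elsewhere the protocol tabulates adverse events (Statistical Considerations item 4), reports all of them to the FDA annually (3.7), documents every serious event whatever its cause (text following the 3.7 tables) and reviews all adverse events in aggregate (5.3).

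**The concern.** Safety is part of the primary objective, and the background says the drug was never tested in patients with ESRD. Three of the listed harms are changes in heart rate or blood pressure, and the protocol already uses the dialysis record as the source for both. Yet the plan names only a pre-dose reading and gives no on-drug value to set against it.

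That leaves the adverse-event route. If section 3.1 is applied, a non-serious slow heart rate does not reach the table. Relatedness is judged by the investigator, and Statistical Considerations item 1 leaves investigators and study staff un-blinded. If all events are recorded instead, detection still depends on someone noticing and reporting one, and the expected counts are too small for the planned test. A measured value taken on a fixed schedule avoids both difficulties.

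**Working it through.** The plan gives no figure of its own on this point, so there is none to reproduce.

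**1. Is there a named on-drug reading?** Where the protocol wants repetition, it says so. Physicals are at screening and Visits 12 and 18, bleeding time is at all visits, and adverse events and access issues are at each visit. Vital signs carry no such instruction. Named readings per completer are therefore 1 (screening), with 0 on drug. Recording at every visit would give 1 + 12 + 6 = 19, of which 12 are on drug.

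**2. Expected cases.** There are 23 ticagrelor and 20 placebo subjects enrolled (Statistical Considerations item 4). Take 6.5% as the middle of the listed 6 to 7%.
- Expected cases: 23 × 0.065 = 1.5.
- Chance of at least one: 1 − 0.935^23 = 0.79.

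**3. Effect of the section 3.1 rule.** Let s be the share of cases judged both serious and related. The documents do not give s. The chance that at least one case is recorded is 1 − (1 − p·s)^23, for p from 0.06 to 0.07:

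| s (assumed) | chance at least one is recorded |
|---|---|
| 0 | 0% |
| 10% | 13 to 15% |
| 25% | 29 to 33% |
| 50% | 50 to 56% |
| 100% | 76 to 81% |

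**4. Power of the planned chi-square test if every case were recorded.** Exact enumeration, uncorrected statistic, two-sided 5%, placebo rate assumed:

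| rates | 23 v 20 | 35 v 35 |
|---|---|---|
| 6.5% v 2% | 1.0% | 10.3% |
| 7% v 3% | 1.1% | 9.3% |

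With no placebo cases, 4 of 23 gives p = 0.0502 and 5 of 23 gives p = 0.027. Significance needs 5/23 = 22%, over three times the listed rate.

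**5. What scheduled readings would add.** For 80% power at two-sided 5%, the detectable mean difference is 2.8 × SD × √(1/n₁ + 1/n₂) × √f. Here f = 1 for one unadjusted reading, f = 1 − ρ² for one reading adjusted for baseline, and f = (1 + 11ρ)/12 − ρ² for the mean of 12 visits adjusted for baseline. SD 10 bpm and equal correlation ρ of 0.5 to 0.7 are assumed.
- √(1/23 + 1/20) = 0.3057, so one unadjusted reading detects 2.8 × 10 × 0.3057 = 8.6 bpm.
- One adjusted reading: 8.56 × √0.75 = 7.4 (ρ = 0.5) to 8.56 × √0.51 = 6.1 (ρ = 0.7).
- Adjusted 12-visit mean: 8.56 × √0.2917 = 4.6 (ρ = 0.5) to 8.56 × √0.235 = about 4.1 (ρ = 0.7). Across SD 8 to 12 the range is 3.3 to 5.5.
- With the protocol's 25% drop-out (about 17 v 15), the adjusted mean detects 5.4 to 4.8 bpm at SD 10.

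**The case against.** **Vital signs may be collected later.** A reader might infer that heart rate and blood pressure are taken only at screening and never on drug. The documents do not support that. The physical examination stands in the same screening list and yet recurs at Visits 12 and 18, and dialysis parameters are promised throughout. Because "All of these visits will occur while the subjects are at their normal dialysis treatment", readings probably exist in the dialysis record and could be extracted afterwards, although availability is not stated. What stands is that no text names them as study data after screening, and none analyses them.

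**The gap in reporting comes mainly from section 3.1.** This is correct. A reader might infer that bradycardia cannot be reported at all, but 3.1 conflicts with the sections that tabulate, report or review adverse events more widely, and adverse events are reviewed at each visit. Reconciling 3.1 would let a bradycardia noted at a visit reach the table. Step 4 shows why that alone would not make the test informative.

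**Bradycardia as the most frequent listed harm.** A reader might infer this from 2.1. It shares the top tier with elevated serum creatinine, and both tiers are minimums, so a harm in the 3% tier, such as bleeding, could be more common.

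**The size of the gain.** Setting 8.6 against 4.1 to 4.6 bpm credits averaging and baseline adjustment together and assumes no drop-out. The fairer contrast is 6.1 to 7.4 bpm for one adjusted reading. A mean difference is also not a bradycardia rate, and the documents give no heart-rate difference that would matter.

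**Pilot status.** Tabulating adverse events is ordinary for a pilot, and the screening blood pressure already serves the eligibility limit. Both are fair, and they are why the addition should be labelled supportive.

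**Conclusion.** The concern holds in a limited form. Heart rate and blood pressure relate to three listed harms and are available from a source already in use, but they have no stated schedule after screening and no place in the analysis. The adverse-event table does not make up for this: the recording rule is contradictory, and even complete recording would leave about 1.5 expected bradycardia cases and about 1% power with 23 v 20.

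The textual finding rests on no assumption. The sizes do. The 6.5% rate is taken from minimums listed for earlier study participants, and the placebo rate, the share s, the SD and the correlation are all assumed. The documents do not show that no on-drug readings exist or that bradycardia would certainly go unreported.

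**What to change.** 1. In Biomedical Research item 1, state that heart rate and blood pressure are copied from the dialysis record at screening and at Visits 1 to 18.
2. In Statistical Considerations item 4, add a supportive comparison by arm of each subject's mean on-drug heart rate, systolic and diastolic blood pressure (Visits 1 to 12), adjusted for the screening value. Use ANCOVA, or a mixed model with a stated simple covariance structure; an unstructured matrix for 12 visits has 12 × 13/2 = 78 parameters for 43 subjects. Report mean differences with 95% CIs and make no multiplicity claim. Summarise Visits 13 to 18 separately as off-drug.
3. Reconcile section 3.1 with Statistical Considerations item 4, section 3.7 with the serious-event text that follows it, and section 5.3, so that one rule states which adverse events are recorded.

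The cost is some extra transcription from a record already used, at visits already held during dialysis, and one supportive analysis. For subjects already enrolled, past values can be extracted if the record holds them. No new procedure or patient is needed, and no treatment or stopping rule changes.

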IRB-HSR# 17224: Randomized, Placebo-controlled, Single Blind, Trial to Determine the Safety and Efficacy of Ticagrelor for Maintaining Patency of Arterio-Venous Fistulae Created for Hemodialysis

► IF YES, who will generate the randomization scheme?

UVa Statistician: [name]

2. What are the statistical considerations for the protocol?

Since Ticagrelor has not been used in hemodialysis patients for the purpose of preventing thrombosis in dialysis vascular accesses (Arterio-Venous Fistulae and Grafts), this study is designed as a pilot study in that patients are randomly assigned to receive Ticagrelor or placebo drug for a six-month treatment period plus an additional 6-month follow-up period. The primary objective is to evaluate the feasibility and safety of Ticagrelor in hemodialysis patients with AVF vascular access. The secondary objective is to evaluate the treatment efficacy in that whether Ticagrelor will preserve patency of hemodialysis vascular access better than Placebo. The study will follow intent-to-treat principle and all randomized patients will be included in the analyses for the primary and secondary objectives.

3. Provide a justification for the sample size used in this protocol.

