- Weekly Hemoglobin Tests

2.3 Under what criteria would an INDIVIDUAL SUBJECT’S study treatment or study participation be stopped or modified

At subject, PI or sponsor’s request

Treatment would be stopped if the subject had a serious adverse event deemed related to study

Subjects will be stopped if they meet one or more of the study stopping rules

2.4 Under what criteria would THE ENTIRE STUDY need to be stopped.

IRB-HSR# 17224: Randomized, Placebo-controlled, Single Blind, Trial to Determine the Safety and Efficacy of Ticagrelor for Maintaining Patency of Arterio-Venous Fistulae Created for Hemodialysis

*These are called stopping rules for early termination of the entire study.
List criteria regardless of whether the study is sponsored or not.
Be sure to include any criteria for which the UVa PI would halt the study at UVa.*

Per IRB, PI, DSMB, or sponsor discretion

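### The bleeding rule can be read as ending study participation, not only study drug, and no available section keeps those patients in stenosis follow-up

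*Combined protocol and SAP*

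**What the plan says.** The rule is in the protocol under Biomedical Research, item 1, below the heading Study Medication Stopping Rules for Prolonged Bleeding. It has three steps.

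- For access bleeding: "If post treatment bleeding time is prolonged more than 30 minutes we will stop the study drug and refer for fistulogram".
- If that does not settle it: "If bleeding still persists after fistulogram and intervention we will continue to hold the study drug and do work up for bleeding". Drug is also held for other signs, including "signs of increased tendency for bleeding as recurrent Epistaxis > twice in one week, if any evidence of GI bleed" and a fall in hemoglobin. No fistulogram referral is attached to these signs.
- Finally: "If the bleeding is believed to be drug related or it no resolution occurs the subject will be withdrawn from the study".

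Data and Safety Monitoring Plan 2.3 uses two different expressions. For a related serious event it says "Treatment would be stopped if the subject had a serious adverse event deemed related to study". For the stopping rules it says "Subjects will be stopped if they meet one or more of the study stopping rules".

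Statistical Considerations, item 2, promises intent-to-treat and says that "all randomized patients will be included in the analyses for the primary and secondary objectives". Item 5 specifies Kaplan-Meier curves, a stratified Cox model and a test: "survival difference between the two arms will be evaluated using a one-sided log-rank test stratified by the history of stenosis". It gives no rule for patients who leave early.

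**The concern.** The heading over the rule suggests that only drug is meant; the sentence itself speaks of the study. Section 2.3 does not decide between them, since a serious drug-related bleed meets both of its lines. Staff following the protocol faithfully could therefore keep or lose the same patient.

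If the literal reading is applied, a withdrawn patient contributes to time to first stenosis only up to last contact. Including every randomized patient in the analysis does not restore events that nobody recorded.

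The loss may also differ by arm. Data and Safety Monitoring Plan 2.1 states a raised risk of severe bleeding on ticagrelor. Statistical Considerations, item 1, leaves investigators and staff un-blinded, so whether a bleed is attributed to drug is judged with the assignment known. At stake is whether the secondary result can be read, in a trial that expects few events.

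**Working it through.** **Planned rates.** Statistical Considerations, item 3, gives one-year stenosis rates of 10% on ticagrelor and 36% on placebo, and a hazard ratio of 0.236. This reproduces: ln(1 - 0.10) / ln(1 - 0.36) = (-0.1054) / (-0.4463) = 0.236.

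**Expected events.** Item 4 reports 23 ticagrelor and 20 placebo patients enrolled.

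- Ticagrelor: 23 x 0.10 = 2.3
- Placebo: 20 x 0.36 = 7.2
- Total: 9.5

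**What a few unseen outcomes can do.** This is an illustration with chosen inputs. Take 2 of 23 against 7 of 20 events, at times uniform over 12 months. Two other ticagrelor patients (2/23 = 8.7%) are withdrawn at uniform times in months 0-6. Each loses 9 of 12 months on average, or (9/12)/23 = 3.3% of ticagrelor person-time. Over 20,000 draws, the median one-sided unstratified log-rank p was:

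| Treatment of the two patients | Median p |
|---|---|
| Both censored at withdrawal | 0.024 |
| Followed, neither has stenosis | 0.018 |
| Followed, one has stenosis | 0.045 |
| Followed, both have stenosis | 0.091 |

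With one later event, p exceeds 0.05 in about a quarter of draws.

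**Bias with no true effect.** The documents give no bleeding-withdrawal rate by arm and no imaging yield, so every input here is an assumption:

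- Both arms have a 36% rate at 12 months.
- 5%, 10% or 25% of ticagrelor patients are withdrawn at uniform times in months 0-6. The top value equals the protocol's allowance for all losses together.
- These patients have k = 1, 2 or 3 times the stenosis hazard of the others.
- Imaging before withdrawal finds either nothing or lesions due within 3 or 6 months.
- The test is one-sided at 5%, stratified by stenosis history (40% prevalence, hazard ratio 2).
- Sample sizes are 35/35 and 23/20, with 25,000 runs per setting.

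| Setting | Type I error |
|---|---|
| k = 1, no image | 4.8-5.3% |
| k = 2-3, no image | 5.7-11.5% |
| k = 1-3, image finds lesions due within 3 months | 3.3-6.2% |
| k = 1-3, image finds lesions due within 6 months | 2.4-4.9% |
| Half the withdrawal rate on placebo, all k and imaging settings | 3.4-7.8% |
| Everyone followed to month 12, all settings | 4.4-5.4% |

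The top of the second row needs 25% withdrawn, all on ticagrelor, three times the hazard and no image. Not modelled: lesions found by an extra image that would never otherwise have surfaced.

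**The case against.** The strongest reply is that the rule concerns drug only. Its heading says so, the intent-to-treat sentence points the same way, and elsewhere the protocol puts participation at one year and says both groups are monitored after treatment. A reader might infer that the plan definitely drops bleeding patients from follow-up. The documents do not support that; they support ambiguity. The consent pages and the opening pages are not in the available text and may bear on it. What stands is that no available section says outcomes are still collected after such a withdrawal.

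A reader might also infer that the rule biases the test towards ticagrelor. That is not established. Material inflation needs withdrawn patients to be at high stenosis risk and not imaged, and these conditions fit together poorly. The documents link bleeding to stenosis through access bleeding, which is sent for fistulogram. The signs without referral have no stated link to stenosis. With imaging the test can be conservative.

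Nor would one missed event usually overturn the result: the median p stays at 0.045. Two would, but if the patients are independent, both developing stenosis has probability 0.10 x 0.10 = 1% at the ticagrelor rate, or 0.36 x 0.36 = 13% at the placebo rate.

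Finally, this is the secondary objective of a pilot, and early withdrawals already go to aggregate review (Data and Safety Monitoring Plan 5.3). That limits the priority of the point. It does not supply the missing outcomes.

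**Conclusion.** The point holds as an ambiguity with a real consequence. Read literally, the rule ends stenosis follow-up for some bleeding patients, possibly more often on ticagrelor, and leaves the intent-to-treat analysis of the secondary outcome only partly deliverable. The direction and size of any bias cannot be determined from the documents. Under the assumed inputs, type I error is near or below 5% in most settings and about 6-12% only with two to three times the hazard and no image. With 9.5 expected events, two unseen ticagrelor events could change the conclusion in the illustration; one would leave it borderline. This is a cheap improvement to a secondary analysis. It does not affect the case for the trial or its primary objective.

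Separately, and minor, prolonged bleeding means more than 20 minutes in the surveillance text and more than 30 minutes in the stopping rules. A reader might take this as a contradiction in the rules. Both thresholds can be applied as triggers, but those passages should be reconciled.

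**What to change.** 1. Reword the bleeding rule and Data and Safety Monitoring Plan 2.3 so that ending study drug does not end outcome follow-up. When drug is held or stopped does not change.
2. Unless the patient withdraws consent, keep collecting adverse events, the monthly access flow, stenosis and interventions to month 12, and analyse as randomized.
3. Report withdrawals by arm and reason.

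No new procedure is needed, because monthly flow and angioplasty are already standard of care. The costs are an IRB modification and some retrospective abstraction for the 43 enrolled. Outcomes of patients already withdrawn may not be recoverable. The comparison will contain more off-drug time for these patients, as it already does for everyone in months 6-12. If drug-only stopping was always intended, the edit simply records it.
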